#### **14. The risks and hazards of lambda interferon therapy**

Lambda has been generally well tolerated in clinical studies. A lower frequency of musculoskeletal (myalgia, arthralgia, and back pain) and flu-like symptoms (chills, pyrexia, and pain) was observed across Phase 2 studies in subjects receiving IFN regimens containing Lambda compared with alfa. In addition, there was a notable lack of hematologic toxicity in the WBC or platelet lineages in subjects receiving Lambda regimens.

Laboratory abnormalities have generally been of low grade and self-limited. When study regimens included concomitant RBV administration, decreases in hemoglobin levels were observed as expected; however, anemia was less frequent and milder with Lambda/RBV than with alfa/RBV. Hematologic toxicity was also reported less frequently in groups treated with Lambda compared with alfa.

The main safety finding associated with Lambda treatment has been the higher frequency of transaminase elevations, accompanied, in some cases, by increases in total and conjugated (direct) bilirubin, but without evidence for impaired liver synthetic function such as decreased albumin or increased INR. The hyperbilirubinemia cases resolved with no laboratory evidence of sustained hepatic dysfunction following dose reduction or discontinuation of study drug.

In one study, 3 cases of concurrent ALT and TBILI elevations in patients with HCV treated with Lambda/RBV/asunaprevir (ASV) met program-defined criteria for pDILI; this led to discontinuation of this regimen in future development plans. Frequencies of concurrent ALT/AST and TBILI elevations across studies were as follows: 18.2% for Lambda/RBV/ASV, 3.6% for Lambda/RBV, 2.3% for alfa-2a/RBV/ASV, and 3.5% for alfa-2a/RBV.

In another study in patients with HBV, 4 subjects (5.0%) in the Lambda 180- $\mu$ g group and 1 subject (7.7%) in the 240  $\mu$ g group, and 1 subject (1.2%) in the alfa group met the laboratory criteria for pDILI. In 5 of the 6 cases, an alternative explanation (early, on-treatment, host-mediated ALT flare) was identified.

15. **The risks of the combination of Lonafarnib, Ritonavir, Lambda Interferon and HBV therapy:** The risk of combination therapy with lonafarnib, ritonavir and lambda interferon are not known. Lonafarnib, in combination with ritonavir was administered along with alpha interferon to 11 patients in the LOWR-2 study in Turkey. In the LIRA-B study, where patient with mono-infection with chronic hepatitis B were randomized to treatment with either interferon alpha or lambda interferon, overall adverse events, serious adverse events and discontinuation rates were comparable between arms however the AE spectra differed, with more cytopenias, flu-like and musculoskeletal symptoms in the alpha group and more ALT flares and bilirubin elevations seen in lambda.

### **Adverse Events and Modification of Dose of Prenylation Inhibitor and Ritonavir**

Patients will be monitored for side effects. The use of statins will be prohibited during the course of the study as are the use of moderate and strong CYP3A inhibitor and inducers. Discontinuation of lonafarnib, ritonavir and lambda interferon will be based upon the scoring of adverse events as shown in table 5. The scoring of toxicity will be performed from the CTCAE Version 4.03 with modifications for leukocytes, platelets, prothrombin time, partial thromboplastin time, ALT, AST and bilirubin. These variables have been modified because the National Cancer Institute (NCI) designed the original version with use for cancer trials and not for clinical trials in liver disease. The modified

version to be utilized for this clinical trial accounts for accepted variations of liver tests used in various other liver disease clinical trials by the Liver Diseases Branch. Factors that will lead to discontinuation of lonafarnib, ritonavir and lambda interferon include pregnancy, any grade 3 or any grade 4 adverse events or any adverse event, which, in the opinion of the investigator, places the patient at increased risk. Drug discontinuation may also be based on individual clinical presentations of each subject. For example, AST and ALT values will be evaluated in the context of each individual's baseline values. Rather than utilizing specific cutoff values, which may not be in the best interest of each subject, if the investigator identifies a significant elevation in liver related laboratory tests which may jeopardize the patient's safety, the drug may be discontinued. This is further defined below. If the female becomes pregnant, the patient's obstetrician will be provided with the standard of care guidelines to prevent HBV transmission. Medications will be stopped if pregnancy occurs, with the exception of HBV therapy, given the risk of hepatitis B flare during pregnancy. Lonafarnib, ritonavir and lambda interferon will not be restarted unless another cause for the abnormality or symptom is found.

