**Table 4: Guidelines for Treatment Interruption or Discontinuation and Dose Modification**

Toxicity	Management, Monitoring, and Dose Modification	Discontinuation of Drug
	Immediate Actions/Resolution	
Adverse Events		

Lambda AE ≥ Grade 3, considered at least possibly related to study drug and clinically significant, and no specific guidance given below
	
Interrupt dosing and monitor weekly
 
Resolution: If event resolves to ≤ Grade 1 or baseline value, restart dosing at DR1
	
If event does not resolve in 2 weeks (missed 2 consecutive doses of drug) or If event recurs at DR1, discontinue drug

Lonafarnib AE ≥ Grade 3, considered at least possibly related to study drug and clinically significant, and no specific guidance given below
	
Interrupt dosing and monitor weekly
 
Resolution: If event resolves to ≤ Grade 1 or baseline value, restart dosing at DR1
	
If event does not resolve in 2 weeks (missed 14 consecutive doses of drug) or If event recurs at DR1, discontinue drug

Toxicity	Management, Monitoring, and Dose Modification	Discontinuation of Drug
Lambda AE $\geq$ Grade 3, considered at least possibly related to study drug and not clinically significant, and no specific guidance given below	Discuss with medical monitor. Not all Grade 3 AEs will require dose modification.	
Lonafarnib AE $\geq$ Grade 3, considered at least possibly related to study drug and not clinically significant, and no specific guidance given below	Discuss with medical monitor. Not all Grade 3 AEs will require dose modification.	
Lambda Depression	See Table 5 and CTCAE neurologic definitions for mild/moderate/severe depression Interrupt dosing. Obtain psychiatric consult	
Lambda New ocular symptoms: New decrease or loss of vision or other clinically significant ocular sign or symptom	Interrupt dosing. Obtain complete eye examination performed by an ophthalmologist. Discuss further management with the medical monitor prior to restarting therapy.	
Hematologic abnormalities		
Lambda		
ANC		
$\geq 750/\text{mm}^3$	Maintain dose	
$< 750/\text{mm}^3$	Interrupt dosing Resolution: If ANC $> 500/\text{mm}^3$ , restart dosing at DR1	If event does not resolve in 4 weeks (missed 4 consecutive doses) or If event recurs (confirmed) at DR1, discontinue drug
Platelets		
$< 40,000$	Reduce dose to DR1	
$< 25,000$		If event is confirmed, discontinue drug

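### For several non-hepatic grade 3 or higher events, the text stops all three drugs without restart, while Table 4 orders interruption, dose reduction or possibly no change

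*Combined protocol and SAP*

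**What the plan says.** Three parts of the protocol bear on this.

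**Adverse Events and Modification of Dose of Prenylation Inhibitor and Ritonavir.** The stopping rule is "Factors that will lead to discontinuation of lonafarnib, ritonavir and lambda interferon include pregnancy, any grade 3 or any grade 4 adverse events". It sets no condition on relatedness, clinical significance or resolution. On grading, the section says: "Discontinuation of lonafarnib, ritonavir and lambda interferon will be based upon the scoring of adverse events as shown in table 5". Liver tests are given as an example of individual judgement, which ends with "This is further defined below". After some text on pregnancy the paragraph closes: "Lonafarnib, ritonavir and lambda interferon will not be restarted unless another cause for the abnormality or symptom is found".

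**Tables 3 to 5.** Table 3 sets one dose-reduction step (DR1): lambda from 180 to 120 µg and lonafarnib from 50 to 25 mg. Table 4 has general rows, one for each of these two drugs, for grade 3 or higher events "considered at least possibly related to study drug and clinically significant, and no specific guidance given below". Dosing is interrupted and, if the event falls to "Grade 1 or baseline value, restart dosing at DR1". The drug is discontinued only if the event has not resolved in 2 weeks or recurs at DR1. For related events judged not clinically significant, the case goes to the medical monitor, with the remark "Not all Grade 3 AEs will require dose modification". For lambda at platelets below 40,000 the action is "Reduce dose to DR1", with discontinuation at a confirmed count below 25,000. Separate lambda rows cover depression and new ocular symptoms. Table 5 supplies the toxicity grades.

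**Endpoint and follow-up text.** Under Primary Safety End Point, discontinuation by the team or the patient counts as failure to tolerate. Monitoring of Patients Discontinuing Therapy treats stopping for intolerance as treatment failure and says that Table 4 defines intolerance.

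**The concern.** A clinician with a patient who has, say, grade 3 diarrhea judged related to lonafarnib finds two instructions. One ends the whole regimen for good. The other pauses lonafarnib and resumes it at 25 mg once the event has settled.

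The first stake is the patient's treatment. The protocol itself describes the risk of this combination as unknown, so the stopping rule should leave no doubt.

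The second stake is the data. Because discontinuation is failure on the primary safety endpoint, and stopping for intolerance is treatment failure, the same clinical course can be counted either way depending on which page was followed.

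**Working it through.** No figure in the plan needs reproducing. The check sets the two rules side by side, using Table 5 for grades where it has them.

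| Situation (non-hepatic) | Adverse Events section | Table 4 |
|---|---|---|
| 1. Related, clinically significant, grade 3 or higher, no row of its own, resolves to grade 1 or baseline within 2 weeks | Stop all three drugs, no restart | Interrupt the drug concerned, restart at DR1 |
| 2. Related, grade 3 or higher, not clinically significant | Stop all three, no restart | Discuss with medical monitor; dose change not always needed |
| 3. Lambda, platelets 25,000 to under 40,000/mm3 (grade 3 in Table 5) | Stop all three, no restart | Reduce lambda to 120 µg and continue |
| 4. Depression or new ocular symptoms on lambda, if grade 3 or higher | Stop all three, no restart | Interrupt and obtain a psychiatric consult or eye examination; the ocular row contemplates restarting |

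Situation 4 is the least sharp. The depression row says nothing on restart, and Table 5 has no ocular row, so ocular grades would come from the general toxicity criteria.

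Four ways to reconcile the texts:

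- *Discontinuation means a temporary hold.* The no-restart sentence rules this out.
- *The exception for another cause covers it.* Situations 1 and 2 are confined by Table 4 to events at least possibly related to study drug. In 3 and 4 the exception helps only where another cause is actually found.
- *The pointer to a later definition hands over to Table 4.* It follows the liver-test example. Even read more widely, it comes before the unqualified no-restart sentence, which still forbids the restart that Table 4 orders.
- *The allowance for individual clinical presentations softens the rule.* It adds grounds for stopping and removes none.

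Where the texts do not clash:

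- Liver tests, where the section leaves stopping to the investigator's judgement.
- Unrelated events, which Table 4's general rows do not address.
- Lambda at a confirmed platelet count below 25,000, which both texts stop.
- Events that fail to resolve or that recur at DR1, where Table 4 also discontinues the drug concerned.

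Size per patient, with the planned enrollment of 26 from the statistical considerations: 1/26 = 0.038, or 3.8 percentage points of the tolerability rate.

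How many patients would be involved cannot be derived. The protocol's background on lonafarnib with ritonavir gives 1 of 18 patients with grade 3 events in LOWR-2, none among 21 in LOWR-3 (once-daily dosing), and 4 patients in LOWR-4 with no denominator. None of these regimens is described as including lambda, and the counts are of any grade 3 event, not only those in the table above.

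**The case against.** The strongest reply is that the intended rule can be inferred. Monitoring of Patients Discontinuing Therapy points directly to Table 4 for intolerance. The disputed paragraph sits under a heading on dose modification and is followed at once by a dose-reduction plan and a table of interruption rules. Read literally, it would leave Table 3 and much of Table 4 without effect for related non-hepatic events. A general statement followed by specific rules is the more natural reading. This largely stands as evidence of intent, so a reader who infers that the protocol leaves the choice of rule wholly open goes too far. It does not remove the contradiction, because the no-restart sentence is unqualified and the same section bases discontinuation on Table 5.

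The reply also says that the affected set is narrow. Transaminase elevation, described as lambda's main safety finding, is outside it. The protocol reports little platelet toxicity with lambda and uses 75,000 as the platelet threshold at entry. Grade 3 events in the cited lonafarnib studies look few. All of this stands and limits the size of the problem.

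Two further inferences are tempting but unsupported. One is that every grade 3 or 4 event is in conflict; the exclusions listed in the check show otherwise. The other, from the precis wording about tolerating the prescribed dose, is that finishing at DR1 counts as failure. The endpoint section names only discontinuation, and a dose set by Table 3 can equally be called prescribed.

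**Conclusion.** The contradiction is real and confined to the four non-hepatic situations. It is an inconsistency between two operative instructions. Neither rule is faulted as a design. Table 4 is probably what the sponsor intends, but the text does not say so and in one sentence says the opposite.

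The consequence is mainly clinical: permanent loss of the whole regimen against continuation, possibly at a reduced dose. For the analysis, each patient classified differently moves tolerability by 3.8 points, assuming 26 enrolled and all in the denominator. A reader might infer that the tolerability result will be seriously distorted. The documents do not support that: they give no event rate for this triple combination, the available figures suggest few cases, and the endpoint is descriptive, with the sample size resting on the virologic response. The point should be fixed because the rule guides patient care and the repair is simple.

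**What to change.** Amend the Adverse Events section to state three things:

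- Grade 3 or 4 events at least possibly related to study drug are managed by Table 4, and Table 5 supplies the grades.
- The no-restart sentence applies only to pregnancy and to cases where Table 4 requires discontinuation.
- Whether grade 3 or 4 events judged unrelated stop therapy, since Table 4's general rows do not cover them.

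In the same amendment, say what happens to ritonavir when lonafarnib is interrupted, reduced or stopped. Neither Table 3 nor Table 4 has a ritonavir row, so deferring to Table 4 alone would leave this unsettled.

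If the sponsor intends the stricter rule, change every conflicting Table 4 row to match it: the general grade 3 or higher rows for both drugs and the lambda rows for platelets, depression and ocular symptoms.

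The cost is an amendment to wording, with no new visits or samples. The real trade-off is one of safety. Deferring to Table 4 loosens the literal stopping rule, while the stricter option permanently ends treatment in more patients. With the risk of the combination unknown, the sponsor should make that choice explicitly.

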**Table 3: Dose reduction plan for Lambda/Lonafarnib intolerability**

Assigned Treatment	Starting Dose	Dose Reduction (DR1)
	Dose	Dose
Lambda	180 µg	120 µg
Lonafarnib	50 mg	25 mg

**Table 4: Guidelines for Treatment Interruption or Discontinuation and Dose Modification**

Toxicity	Management, Monitoring, and Dose Modification	Discontinuation of Drug
	Immediate Actions/Resolution	
Adverse Events		

Lambda AE ≥ Grade 3, considered at least possibly related to study drug and clinically significant, and no specific guidance given below
	
Interrupt dosing and monitor weekly
 
Resolution: If event resolves to ≤ Grade 1 or baseline value, restart dosing at DR1
	
If event does not resolve in 2 weeks (missed 2 consecutive doses of drug) or If event recurs at DR1, discontinue drug

Lonafarnib AE ≥ Grade 3, considered at least possibly related to study drug and clinically significant, and no specific guidance given below
	
Interrupt dosing and monitor weekly
 
Resolution: If event resolves to ≤ Grade 1 or baseline value, restart dosing at DR1
	
If event does not resolve in 2 weeks (missed 14 consecutive doses of drug) or If event recurs at DR1, discontinue drug

Toxicity	Management, Monitoring, and Dose Modification	Discontinuation of Drug
Lambda AE $\geq$ Grade 3, considered at least possibly related to study drug and not clinically significant, and no specific guidance given below	Discuss with medical monitor. Not all Grade 3 AEs will require dose modification.	
Lonafarnib AE $\geq$ Grade 3, considered at least possibly related to study drug and not clinically significant, and no specific guidance given below	Discuss with medical monitor. Not all Grade 3 AEs will require dose modification.	
Lambda Depression	See Table 5 and CTCAE neurologic definitions for mild/moderate/severe depression Interrupt dosing. Obtain psychiatric consult	
Lambda New ocular symptoms: New decrease or loss of vision or other clinically significant ocular sign or symptom	Interrupt dosing. Obtain complete eye examination performed by an ophthalmologist. Discuss further management with the medical monitor prior to restarting therapy.	
Hematologic abnormalities		
Lambda		
ANC		
$\geq 750/\text{mm}^3$	Maintain dose	
$< 750/\text{mm}^3$	Interrupt dosing Resolution: If ANC $> 500/\text{mm}^3$ , restart dosing at DR1	If event does not resolve in 4 weeks (missed 4 consecutive doses) or If event recurs (confirmed) at DR1, discontinue drug
Platelets		
$< 40,000$	Reduce dose to DR1	
$< 25,000$		If event is confirmed, discontinue drug

Toxicity	Management, Monitoring, and Dose Modification	Discontinuation of Drug
Hepatobiliary abnormalities  Lambda		
ALT/AST/TBILI $\geq$ CTCAE grade 2	Repeat tests within 48-72 hours and monitor weekly. Monitor ALT, AST, TBili, DB, Albumin, PT/INR Involve medical monitor  Resolution: CTCAE <grade 2, return to routine monitoring.	
ALT/AST $\geq$ CTCAE grade 3	Interrupt dosing  Monitor ALT, AST, TBILI, DB, albumin, PT/INR weekly Involve medical monitor  Resolution: If ALT/AST <CTCAE grade 3, restart dosing at DR1 if agreed upon with medical monitor with weekly monitoring for the first 4 weeks. If stable after 4 weeks of monitoring can resume regular per protocol monitoring.	If event does not resolve in 4 weeks (missed 4 consecutive doses) or If event recurs (confirmed) at DR1, discontinue drug
TBILI $\geq$ CTCAE grade 3	Interrupt dosing  Monitor ALT, AST, AP, TBILI, DB, albumin, PT/INR weekly Involve medical monitor  Resolution: If TBILI $\leq$ CTCAE grade 3, restart dosing at DR1 if agreed upon with medical monitor with weekly monitoring for the first 4 weeks. If stable after 4 weeks of monitoring can resume regular per protocol monitoring.	If event does not resolve in 2 weeks (missed 2 consecutive doses) or If event recurs (confirmed) at DR1, discontinue drug
Lonafarnib		
ALT/AST/TBILI $\geq$ CTCAE grade 2	Repeat tests within 48-72 hours and monitor weekly. Monitor ALT, AST, TBili, DBili, Albumin, PT/INR Involve medical monitor  Resolution: CTCAE <grade 2, return to routine monitoring.	
ALT/AST $\geq$ CTCAE grade 3	Interrupt dosing  Monitor ALT, AST, TBILI, DB, albumin, PT/INR weekly Involve medical monitor  Resolution: If ALT/AST <CTCAE grade 3, restart dosing at DR1 if agreed upon with medical monitor with weekly monitoring for the first 4 weeks. If stable after 4 weeks of monitoring can resume regular per protocol monitoring.	If event does not resolve in 2 weeks (missed 14 consecutive doses) or If event recurs (confirmed) at DR1, discontinue drug

Toxicity	Management, Monitoring, and Dose Modification	Discontinuation of Drug
TBILI $\geq$ CTCAE grade 3	Interrupt dosing  Monitor ALT, AST, AP, TBILI, DB, albumin, PT/INR weekly Involve medical monitor  Resolution: If TBILI <CTCAE grade 3, restart dosing at DR1 if agreed upon with medical monitor with weekly monitoring for the first 4 weeks. If stable after 4 weeks of monitoring can resume regular per protocol monitoring.	If event does not resolve in 2 weeks (missed 14 consecutive doses) or If event recurs (confirmed) at DR1, discontinue drug
Renal function abnormalities ( lonafarnib AND lambda )		
Creatinine clearance < 50 mL/min		Discontinue drug

**In addition to the above rules, all subjects who meet criteria for a treatment related liver event will undergo the following clinical work up:**

- Ultrasound of the liver should be performed, including doppler, for subjects with a bilirubin level greater than 1.5 times baseline
- If clinically feasible, a liver biopsy should be performed.
  - o When a percutaneous biopsy is contraindicated, a transjugular biopsy may be discussed.
- Liver and chemistry labs should be performed weekly (minimally include ALT, AST, bilirubin, INR, alkaline phosphatase, albumin and gamma-GT) until the bilirubin returns to baseline value.
- HBV DNA and HDV RNA should be monitored weekly
- 5 ml of serum plus 5 ml of plasma should be collected for possible later biomarker analysis
- Autoimmune markers (antinuclear antibody [ANA], anti-smooth muscle antibody [anti-SMA], anti-LC1, anti-SLA liver kidney microsome type 1 and type III antibody [anti-LKM1,3]),
- \_C3, C4 and CH50,
- \_Acute viral hepatitis,
  - o Serologies for acute hepatitis A and E (IgM);
  - o PCR for HCV, hepatitis E (stool and blood),
  - o *Cytomegalovirus* (CMV), PCR
  - o *Epstein-Barr virus* (EBV), PCR
  - o Herpes simplex viruses 1 and 2 (HSV), PCR
- \_Review of pre-existing hepatic disease (excluding HBV),

- Review of concomitant medication(s), or herbal medications and substances known to be hepatotoxic, tests for alcohol and acetaminophen and drugs of abuse, if indicated

**Table 5. Scoring of toxicity for dose modification.** Scoring of toxicity from the CTCAE Version 4.03, with modifications for leukocytes, platelets, prothrombin time, partial thromboplastin time, ALT, AST and bilirubin. Normal ranges for values at the NIH Clinical Center are used.

Scoring of toxicity for dose modification						
		Grade				
Adverse Event	Short Name	1	2	3	4	5
Allergic reaction/hypersensitivity (including drug fever)	Allergic reaction	Transient flushing or rash; drug fever <38 C (<100.4 F)	Rash; flushing; urticarial; dyspnea; drug fever >38 C (>100.4 F)	Symptomatic bronchospasm, with or without urticarial; parenteral medication(s) indicated; allergy-related edema/angioedema; hypotension	Anaphylaxis	Death
Anorexia	Anorexia	Loss of appetite without alteration in eating habits	Oral intake altered without significant weight loss or malnutrition; oral nutritional supplements indicated	Associated with significant weight loss or malnutrition (e.g., inadequate oral caloric and/or fluid intake); IV fluids, tube feedings or TPN indicated	Life threatening consequences	Death
Nausea	Nausea	Loss of appetite without alteration in eating habits	Oral intake decreased without significant weight loss, dehydration or malnutrition;	Inadequate oral caloric or fluid intake; IV fluids, tube feedings, or TPN indicated >24 hrs	Life threatening consequences	Death

			IV fluids indicated <24 hrs			
Fatigue (asthenia, lethargy, malaise)	Fatigue	Mild fatigue over baseline	Moderate or causing difficulty performing some ADL	Severe fatigue interfering with ADL	Disabling	-----
Diarrhea	Diarrhea	Increase of <4 stools per day over baseline; mild increase in ostomy output compared to baseline	Increase of 4-6 stools per day over baseline; IV fluids indicated <24 hrs; moderate increase in ostomy output compared to baseline; not interfering with ADL	Increase of >6 stools per day over baseline; incontinence; IV fluids >24 hrs; hospitalization ; severe increase in ostomy output compared to baseline; interfering with ADL	Life threatening consequences (e.g. hemodynamic collapse)	Death
Distention/bloating, Abdominal	Distention	Asymptomatic	Symptomatic, but not interfering with GI function	Symptomatic interfering with GI function	-----	-----
Vomiting	Vomiting	1 episode in 24 hrs	2-5 episodes in 24 hrs; IV fluids indicated <24 hrs	>5 episodes in 24 hrs; IV fluids, or TPN indicated >24 hrs	Life threatening consequences	Death
Depression	Depression	Mild depressive symptoms	Moderate depressive symptoms, limiting instrumental ADL	Severe depressive symptoms, limiting self care ADL, hospitalization not indicated	Life threatening consequences, threats of harm to self or others, hospitalization indicated	Death
Creatinine	Creatinine	>ULN – 1.5 X ULN	> 1.5 – 2.0 X ULN	> 2.0 – 6.0 X ULN	>4.0 X ULN	Death

Glomerular Filtration Rate	GFR	<75-60% LLN	<60-40% LLN	<40% LLN, chronic dialysis not indicated	Chronic dialysis or renal transplantation indicated	Death
Glucose, serum-low (hypoglycemia)	Hypoglycemia	<LLN – 55 mg/dL <LLN – 3.0 mmol/L	<55 – 40 mg/dL <3.0 – 2.2 mmol/L	<40-30 mg/dL <2.2-1.7 mmol/L	<30 mg/dL <1.7 mmol/L	Death
Triglyceride, serum-high (hypertriglyceridemia)	Hypertriglyceridemia	>ULN – 2.5 X ULN	>2.5 – 5.0 X ULN	>5.0 – 10 X ULN	>10 X ULN	Death
Cholesterol, serum high (Hypercholesterolemia)	Hypercholesterolemia	>ULN - 300 mg/dL; >ULN - 7.75 mmol/L	>300 - 400 mg/dL; >7.75 - 10.34 mmol/L	>400 - 500 mg/dL; >10.34 - 12.92 mmol/L	>500 mg/dL; >12.92 mmol/L	-----
Pain – Headache	Pain – Headache	Mild pain not interfering with function	Moderate pain; pain or analgesics interfering with function, but not interfering with ADL	Severe pain; pain or analgesics severely interfering with ADL	Disabling	-----
Pain – Abdominal	Pain – Abdominal	Mild pain not interfering with function	Moderate pain; pain or analgesics interfering with function, but not interfering with ADL	Severe pain; pain or analgesics severely interfering with ADL	Disabling	-----
Infection- Upper Airway NOS	Infection – Upper Airway NOS	Mild	Moderate	Severe	Life – threatening; disabling	Death
Infection – Nasopharyngitis	Infection – Nasopharyngitis	Mild	Moderate	Severe	Life-threatening; disabling	Death
Hemoglobin	Hemoglobin	<LLN – 10.0 g/dL	< 10.0 – 8.0 g/dL	<8.0 – 6.5 g/dL	<6.5 g/dL	Death

		<LLN – 6.2 mmol/L <LLN – 100 g/L	<6.2 – 4.9 mmol/L <100 – 80 g/L	<4.9 – 4.0 mmol/L <80 – 65 g/L	<4.0 mmol/L <65 g/L	
Granulocytes	Granulocytes					
Leukocytes (total WBC)	Leukocytes	<2000/mm  <2.0 X 10  /L	<1500 – 1000/mm  <1.5 – 1.0 X 10  /L	<1000 – 500/mm  1.0 – 0.5 X 10  /L	<500/mm  <0.5 X 10  /L	Death
Platelets	Platelets	<70,000/mm  -60,000/mm  <70.0 – 60.0 X 10  /L	<60,000 – 40,000/mm  <60.0 – 40.0 X 10  /L	<40,000 – 25,000/mm  <40.0 – 25.0 X 10  /L	<25,000/mm  <25.0 X 10  /L	Death
INR (International Normalized Ratio of prothrombin time)	INR	>1 – 1.5 X ULN	>1.5 – 2 X ULN	>2 X ULN	-----	-----
PTT Partial Thromboplastin time)	PTT	>1 – 1.5 X ULN	>1.5 – 2 X ULN	>2 X ULN	-----	-----
Bicarbonate, serum-low	Bicarbonate, serum-low	<LLN – 18 mmol/L	<18 – 15 mmol/L	<15-11 mmol/L	<11 mmol/L	Death
Acidosis (metabolic or respiratory)	Acidosis	pH < normal, but >7.3	-----	pH <7.3	pH <7.3 with life threatening consequences	Death
Alkaline Phosphatase (U/L)	Alkaline Phosphatase	>ULN – 2.5 X ULN	>2.5 0 5.0 X ULN	>5.0 – 20.0 X ULN	>20.0 X ULN	-----
Bilirubin (hyperbilirubinemia)	Bilirubin	>ULN – 1.5 X ULN	>1.5 – 3.0 X ULN	>3.0 – 10.0 X ULN	>10.0 X ULN	-----
Albumin, serum-low (hypoalbuminemia)	Hypoalbuminemia	<LLN – 3 g/dL <LLN – 30 g/L	<3 – 2 g/dL <30 – 20 g/L	<2 g/dL <20 g/L	-----	Death
AST, SGOT (serum glutamic	AST	>3 – 5 X patient's baseline values	>5-10 X patient's baseline values	>10 – 20 X patient's baseline values	>20 X patient's baseline values	Death

oxaloacetic transaminase)						
ALT, SGPT (serum glutamic pyruvic transaminase)	ALT	>3-5 X patient's baseline values	>5-10 X patient's baseline values	>10 – 20 X patient's baseline values	>20 X patient's baseline values	Death
Pancreatitis	Pancreatitis		Enzyme elevation or radiologic finding only	Severe pain; vomiting; medical intervention indicated (e.g., analgesia, nutritional support)	Life-threatening consequences; urgent intervention indicated	Death

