### **Initiation of Treatment**

All patients will be initiated on lonafarnib 50 mg orally twice daily, ritonavir 100 mg orally twice daily and lambda 180 mcg subcutaneously weekly. Eiger BioPharmaceuticals, Inc will supply the lonafarnib, ritonavir and lambda interferon under a clinical trials agreement. Patients will be initiated on therapy one or two days after the liver biopsy and will remain in the clinical center for 72 hours after induction of therapy for observation of side effects, administration of medication, and timed blood draws to facilitate analysis of virological response kinetics and pharmacokinetic analysis. During the admission, frequent blood sampling will be performed (0, 6, 12, 18, 24, 36, 48 and 72 hours after, the first dose) for viral kinetics, pharmacokinetics and storage.

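### Table 4 halves the lonafarnib dose count, as printed lets lambda restart at the bilirubin grade that interrupts it, and conflicts with the protocol text on grade 3 and 4 events

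*Combined protocol and SAP*

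**What the plan says.** The section Initiation of Treatment fixes the schedule: "All patients will be initiated on lonafarnib 50 mg orally twice daily", with lambda injected once a week.

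Table 4 pairs a time limit with a count of missed doses.

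- **Lonafarnib.** The general adverse event row has "If event does not resolve in 2 weeks (missed 14 consecutive doses of drug". The ALT/AST and total bilirubin rows both have "If event does not resolve in 2 weeks (missed 14 consecutive doses".
- **Lambda.** The general row has "If event does not resolve in 2 weeks (missed 2 consecutive doses of drug", and the bilirubin row gives the same pair. The neutrophil and ALT/AST rows have "If event does not resolve in 4 weeks (missed 4 consecutive doses".

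On restarting lambda, the bilirubin row interrupts at grade 3 or above and then says "If TBILI $\leq$ CTCAE grade 3, restart dosing at DR1 if agreed upon with medical monitor". The ALT/AST rows for both drugs say "If ALT/AST <CTCAE grade 3, restart dosing at DR1 if agreed upon with medical monitor", and the lonafarnib bilirubin row also requires below grade 3. The neutrophil row keeps the dose at 750/mm³ or above, interrupts below that, and then says "If ANC $> 500/\text{mm}^3$ , restart dosing at DR1".

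Outside the table, the section Adverse Events and Modification of Dose of Prenylation Inhibitor and Ritonavir lists any grade 3 or grade 4 event among the reasons for discontinuing all three drugs, and bars a restart unless another cause is found. Monitoring of Patients Discontinuing Therapy names Table 4 as the definition of intolerance. Primary Safety End Point counts discontinuation, by the clinical team or the patient, as failure to tolerate treatment.

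**The concern.** These rules decide who is re-dosed after a toxicity and who is permanently stopped, and stopping is the failure event of the primary safety endpoint. Each should therefore have one reading.

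The lonafarnib limit gives two periods that differ twofold. The lambda bilirubin limit, as printed, lets dosing resume while the abnormality that stopped it is still present. That matters for this drug. The protocol's own account of lambda's risks puts transaminase elevations first, in some cases with bilirubin rises. It reports 3 patients with jaundice in the lambda monotherapy study in hepatitis D and describes the risk of the present combination as unknown. Finally, the text and the table send a patient with a grade 3 event to opposite outcomes: permanent discontinuation, or restart at the reduced dose.

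**Working it through.** **1. Dose counts.** Doses missed = doses per day × days.

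| Drug and limit | Schedule | Computed | Printed | Agrees |
|---|---|---|---|---|
| Lonafarnib, 2 weeks (3 rows) | 2 per day | 2 × 14 = 28 | 14 | No |
| Lambda, 2 weeks (general, bilirubin) | 1 per 7 days | 14 / 7 = 2 | 2 | Yes |
| Lambda, 4 weeks (neutrophils, ALT/AST) | 1 per 7 days | 28 / 7 = 4 | 4 | Yes |

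The printed 14 cannot be reproduced from the trial's schedule. It would need once-daily dosing (1 × 14 = 14). At twice daily, 14 doses last 14 / 2 = 7 days, and the ratio is 28 / 14 = 2. All four lambda pairs agree and none of the three lonafarnib pairs does, so the bracket is evidently meant as an equivalent of the time limit and is miscounted. A lonafarnib event that resolves after day 7 but within day 14 may restart at 25 mg under the time limit, but is past the limit under the dose count.

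**2. Grade 3 liver rows.** Compare the values that interrupt dosing with those that allow a restart.

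| Row | Interrupt | Restart | Overlap |
|---|---|---|---|
| Lambda ALT/AST | ≥ grade 3 | < grade 3 | None |
| Lambda bilirubin | ≥ grade 3 | ≤ grade 3 | All of grade 3 |
| Lonafarnib ALT/AST | ≥ grade 3 | < grade 3 | None |
| Lonafarnib bilirubin | ≥ grade 3 | < grade 3 | None |

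Table 5 defines grade 3 bilirubin as more than 3.0 and up to 10.0 times the upper limit of normal. The restart condition is labelled as resolution, and the next column discontinues only for an event that has not resolved within 2 weeks. As printed, bilirubin that stays at grade 3 is already resolved. It may therefore be re-dosed at 120 µg if the medical monitor agrees, and it does not trigger the 2-week stop.

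**3. Text against table.** Take a clinically significant grade 3 event, at least possibly related to lonafarnib, with no other cause found and no specific row.

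- *Adverse event section:* all three drugs are discontinued and not restarted.
- *Table 4:* lonafarnib is interrupted and restarted at 25 mg once the event falls to grade 1 or baseline.

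For grade 3 events that are not clinically significant, Table 4 requires only a discussion with the medical monitor. The text makes no such distinction.

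**4. Lambda neutrophils.** Interrupt below 750/mm³ and restart above 500/mm³: counts of 501 to 749 satisfy both. The row stops the drug if the event *recurs* at the reduced dose, but does not say what recurrence means for a patient who restarted while still below 750.

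**The case against.** **Dose count.** The operative test is failure to resolve within 2 weeks, and the count is a bracketed gloss. The general row also orders weekly monitoring, so on the dose-count reading lonafarnib would be stopped for good at about the first weekly check. This stands. A reader might infer two equally valid stopping rules, or a safety hazard. The documents support neither: the lambda rows show the bracket is an equivalent, and the shorter reading stops the drug sooner. What remains is a wrong number that staff, who track doses by diary and pill count, could apply literally.

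**Bilirubin sign.** The point rests on one character in a table converted from PDF. Restart also needs the medical monitor's agreement and weekly checks for 4 weeks. Both points stand, so the source must be checked first. If the sign is printed there, it is probably a slip, but it is still a re-dosing limit.

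**Text against table.** Table 4 is named as the definition of intolerance, and a dose-reduction plan would have little use if every grade 3 event ended treatment. Table 4 is therefore the likelier governing text. However, the text's pointer to further definition below follows its remarks on liver tests, and no sentence gives Table 4 precedence over the bar on restarting.

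**Neutrophils.** A reader might infer that this row is simply wrong. The documents do not show that. Holding 180 µg below 750 and resuming 120 µg above 500 is workable, because the restart dose is lower. Only the lack of an explicit statement and the undefined recurrence stand. Such cases are probably few, since the protocol reports little white-cell toxicity with lambda.

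**Conclusion.** The concern holds in this form. The lonafarnib dose count is wrong by a factor of 2 in all three rows that state one. Its safety effect is small, but it bears on who may restart. The lambda bilirubin restart limit, if the source prints what the converted text shows, admits the whole of grade 3, in one of four grade 3 liver rows. The conflict between the adverse event section and Table 4 is real and unresolved by any stated precedence. It carries the most weight for the primary safety endpoint, because it decides who is discontinued. The neutrophil row needs clarification only.

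A reader might infer that the tolerability result is materially undermined. The documents do not support that. Each reclassified patient among the planned 26 would move the observed rate by 1/26 = 3.8 percentage points, but neither the endpoint section nor the statistical section gives a tolerability threshold or test for such a shift to change. Nor can the number affected be derived. With lonafarnib plus ritonavir the protocol reports grade 3 events in 1 of 18 patients in LOWR-2, in 4 patients in LOWR-4 (denominator not given) and in none of 21 in LOWR-3, and the present combination is new. The sample size is unaffected.

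The conclusion assumes twice-daily lonafarnib up to the interruption. Table 3 gives the reduced dose as 25 mg and states no change in frequency.

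**What to change.** In one amendment:

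1. Change 14 to 28 missed doses in the three lonafarnib rows of Table 4, keeping 2 weeks as the operative limit.
2. Check the sign in the lambda bilirubin row against the source document, and set the restart to below grade 3, as in the other three grade 3 liver rows.
3. Add one sentence to the adverse event section stating that grade 3 and 4 events are managed by Table 4.
4. In the lambda neutrophil row, either set the restart at 750/mm³ or above, or state that 500 to 749/mm³ is acceptable at 120 µg and define recurrence at that dose. Do not lower the interruption limit to 500/mm³: that would keep patients on full-dose lambda at counts that now stop it, and nothing in the documents supports it.

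The cost is five table cells and one sentence, with no added visits, tests or staff. Item 3 is more than an edit. It chooses between permanent discontinuation and restart after a grade 3 or 4 event in a study under an IND, so the sponsor should make that choice explicitly.
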